**NCT03319173**

**15 September 2017**

## STUDY PROTOCOL

Title of Study: **Dietary Ketosis a Metabolic Sister to Calorie Restriction (CR): Fatty acids activate AMPK energy circuits modulating global methylation via the SAM/SAH axis**

Principle Investigator: [name], CFMP, LPCC

- Protocol Number: Bristlecone-001
- Protocol Date: 09/15/2017 – 05/15/2018
- Version #1
- Investigators: [name] (Principle Investigator)

[name] (Sub-investigator)

- Bristlecone Health, Inc.  
[name]  
[name]  
[contact]

[www.bristleconemedical.com](http://www.bristleconemedical.com)

- Source of external funding: N/A
- Hypothesis or Study Synopsis:

Nutritional epigenetics denotes gene–diet interactions and highlights the modulatory role of nutrition in aging and age-related diseases such as cancer, CVD, diabetes and neurodegenerative disorders. Nutrients are a source of epigenetic modification; they are able to regulate the placement of histone modifiers distinguishing phenotype from genotype. The energy status of the cells (fed or fasted) modulates the regulation of global DNA methylation via the S-adenosylmethionine (SAM), the methyltransferase inhibitor, S-adenosylhomocysteine (SAH) axis and whole blood histamine levels. Insulin resistance and hyperinsulinemia dysregulate cellular signals leading to metabolic inflexibility. Chronic elevations in insulin with long-standing impairments in glucose delivery are associated with profound changes in epigenetic patterns due to over-activation of the mTOR kinase pathway and repression of AMPK. Dietary ketosis is known to change the metabolic status of the cells by increasing the AMP/ATP ratio. AMPK activation adapts rRNA synthesis away from growth/biosynthesis and toward ATP availability and utilization, thereby, attenuating the progression of hypo-metabolic diseases in the body and the brain at the level of the genome.

The study will explore whether early stage memory loss (SMC & MCI) and the comorbidity of Metabolic Syndrome are symptomatic of peripheral and cerebral cellular hypo-metabolism induced by chronic insulin resistance. We will attempt to show that consequential to systemic hyperinsulinemia, aberrant crosstalk between the mitochondria and nuclear genome results in the dysregulation of the regulatory kinases mediating metabolic state and intracellular/extracellular signaling: mTOR and AMPK. The suppression of AMPK signals with chronic overexpression of

mTOR signaling will adapt rRNA synthesis away from nutrient availability and toward ATP consuming processes: the biosynthesis of cholesterol, triglycerides, glycogen with inhibition of fatty acid oxidation, histone acetylation with a down-regulation of NAD+ and SAHH cofactors leading to global DNA hypo-methylation and local hyper-methylation, suppression of the SAM/SAH ratio, the inhibition of SIRT (sirtuin) expression and normalized whole blood histamine levels. These epigenetic shifts mediate global metabolic inflexibility by channeling fuel substrates toward cytosolic, substrate level phosphorylation (SLP) via over expression of the glycolytic enzymes including PDK (pyruvate dehydrogenase kinase) and away from mitochondrial oxidation mediated by the suppression of PDC (pyruvate dehydrogenase complex), the major regulatory gateway of metabolism between glycolysis and citric acid cycle. We will attempt to show that activation of the AMPK pathway via induced and controlled dietary ketosis will inhibit mTOR signaling away from the biosynthesis of energy and SLP toward the generation of ATP by increasing the cellular AMP/ATP ratio, thus regulating oxidative metabolic signals and attenuating global, cellular hypo-metabolism evidenced by marked reductions in lipid synthesis and LP-IR score (particle concentration and size), HgA1c, fasting insulin/HOMA-IR, blood ketones, fasting triglycerides together with epigenetic regulation of DNA methylation status including normalized whole blood histamine levels and homo-cysteine regulation. Improvement in cerebral glucose metabolism and corresponding diagnosis of SMC/MCI will be assessed by the objective changes in the outcome measures of MoCA, BVMT-R (Brief Visual Memory Test-Revised) and Rey Auditory Verbal Learning Task (RAVLT), administered at baseline and weeks 2/4/6/8/10/12.

**Research Question:** Are selective memory complaints (SMC), mild cognitive impairment (MCI) and comorbidity of Metabolic Syndrome symptomatic of peripheral and cerebral hypo-metabolism with corresponding epigenetic shifts in global DNA hypo-methylation/histone acetylation away from nutrient availability and toward biosynthesis with up-regulation of substrate level phosphorylation (SLP) initiated by sustained metabolic inflexibility (hyperinsulinemia), over-activation of the mTOR kinase pathway, and repression of mitochondrial oxidation via inhibition of pyruvate dehydrogenase complex (PDC)?

- Background:

[name], CFMP, LPCC

## Study Goals and Objectives

Primary objectives:

1. Improve cerebral and peripheral substrate oxidation as measured by cognitive assessments (MoCA, BVMT-R & RAVLT) and improved blood lipids (reduction in small LDL particle size)
2. Normalizing the SAM/SAH ratio and whole blood histamine levels to restore global DNA methylation for disease prevention
3. Restoration and balancing of the AMPK/mTOR pathways for disease prevention
4. Alleviate insulin resistance in order to reverse T2DM
5. Restore cerebral glucose metabolism in order to prevent neuron death
6. Prevent cardiovascular disease by restoring metabolic flexibility through fatty acid oxidation

Secondary objectives:

1. Improved self-efficacy; empowerment to normalize blood lipids through nutritional interventions
2. Reduction in depression and anxiety associated with metabolic syndrome
3. Reduction in weight, BMI, body fat mass, HgA1c and normalized blood pressure

Subject Selection:

- The study subjects are adults (18-80) referred by their physician and previously diagnosed with MetS and/or T2DM as measured by possessing at least 2 of the following physiological measures: type II diabetes, BMI >30, HgA1c > 5.7, waist/height ratio >.6, fasting glucose > 125. All subjects will volunteer for the study after being referred by their healthcare provider; they will be randomly assigned to one of two groups: experimental group with induced and controlled dietary ketosis or control group with standard American diet. Participants in both groups will also be required to play PEAK brain training games on iPhone, iPad or Android devices for 120 minutes per week.
- The study will include at least 30 subjects (15 per group) but no more than 80 subjects (40 per group).
- Men and women only (ages 18-80)

Inclusion/Exclusion criteria:

*Inclusion criteria:*

- Male or Female (age 18-80)
- Previously diagnosed with MetS and/or T2DM as measured by possessing at least 2 of the following physiological measures: type II diabetes, BMI >30, HgA1c > 5.7, waist/height ratio >.6, fasting glucose > 125
- Subjective Memory Complaints (SCM) – Subjects score  $\geq 3$  ‘yes’ answers on the Subjective Memory Complaints Questionnaire at the initial visit
- Previously diagnosed with Mild Cognitive Impairment (MCI)

*Exclusion criteria:*

- Previously diagnosed with Alzheimer's disease (AD), dementia or Parkinson's disease

#### RESEARCH METHOD:

Analyses of variance (ANOVA) will be run to assess differences between the experimental and control group. The ANOVA will be run on both groups measuring baseline and post program (week 0 and week 12) HgA1c, fasting insulin, fasting glucose, NMR particle size testing and a methylation profile, which includes: SAM/SAH ratio test and whole blood histamine.

An ANOVA will be run on both groups measuring blood ketones and fasting triglycerides at weeks 0, 3, 6, 9 and 12. The

ANOVA will also be run on both groups measuring cognitive measures using the Rey Auditory Verbal Learning Task, BVMT-R and MoCA assessments at weeks 0 and 12. Mean scores will be used to assess significant differences between the two groups. Further analyses of possible treatment effects will be examine within-group differences using a paired sampled *t*-test.

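### ANOVA with no baseline covariate and no log scale keeps its type I error but is likely to lose power for fasting insulin, triglycerides and SAM/SAH

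*Protocol*

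**What the plan says.** The Research Method section of the protocol gives the whole analysis. For the laboratory measures, it plans ANOVA on both groups at weeks 0 and 12 for "HgA1c, fasting insulin, fasting glucose, NMR particle size testing and a methylation profile, which includes: SAM/SAH ratio test and whole blood histamine". For the repeated measures: "An ANOVA will be run on both groups measuring blood ketones and fasting triglycerides at weeks 0, 3, 6, 9 and 12". One more sentence, directly after the cognitive tests, reads "Mean scores will be used to assess significant differences between the two groups". Within each group the plan examines "within-group differences using a paired sampled *t*-test".

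The section names no transformation, rank method or baseline covariate. It also does not say that values will be analysed untransformed.

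In Study Goals and Objectives, SAM/SAH belongs to primary objective 2 and insulin resistance to primary objective 4. Subject Selection sets the size: "The study will include at least 30 subjects (15 per group) but no more than 80 subjects (40 per group".

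**The concern.** Fasting insulin, triglycerides and a concentration ratio are all positive quantities. If they are right-skewed, a difference in arithmetic means is an inefficient contrast, and a subject with a high starting value carries much of the variance of the change. Entry requires any two of five criteria, so diabetic and non-diabetic subjects can be mixed, which could widen the spread.

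The week-0 value is already collected. Comparing change instead of adjusting for it wastes part of what it offers. At the permitted minimum of 15 per group there is little power to spare: at an assumed two-sided 5% level and 80% power, the detectable difference is (1.96 + 0.84) × √(2/15) = 1.02 SD. At 40 per group it is 0.63 SD. A real effect on measures that serve two primary objectives could therefore be missed because of the choice of method.

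**Working it through.** **Stated figure.** There is none to reproduce. The protocol gives no alpha, power, effect size, SD or distribution for any laboratory measure.

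**Inputs from the protocol.** Two equal groups of 15 to 40; weeks 0 and 12; ANOVA.

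**Inputs assumed.** Log-normal values; log-SD *s* of 0.3 to 0.8; a true 30% reduction; correlation 0.6 between log week-0 and log week-12 values; two-sided 5%.

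**What the planned analysis tests.** With two groups and two visits, the group-by-time term of an ANOVA is equivalent to a t-test on change from week 0. That is the reading used here.

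**Hand check of the log-scale, baseline-adjusted analysis, 15 per group.**
- Effect: |ln 0.7| = 0.357.
- Residual SD: *s* × √(1 − 0.6²) = 0.8*s*.
- Standard error: 0.8*s* × √(2/15) = 0.292*s*.
- Effect divided by standard error: 3.05 (*s* = 0.4), 2.03 (0.6), 1.53 (0.8).
- Critical t on 27 degrees of freedom: 2.05.
- Approximate power: Φ(3.05 − 2.05) = 84%, Φ(2.03 − 2.05) = 49%, Φ(1.53 − 2.05) = 30%.

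Simulation gives 83%, 49% and 31%, in agreement.

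**Simulated power, 15 per group, 30% reduction** (good to about one or two points):

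| Log-SD | Raw change | Log change | Raw, baseline-adjusted | Log, baseline-adjusted |
|---|---|---|---|---|
| 0.4 | 61% | 76% | 78% | 83% |
| 0.6 | 29% | 43% | 40% | 49% |
| 0.8 | 16% | 27% | 22% | 31% |

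The gain from first to last column is 22, 20 and 15 points. Both the log scale and the covariate contribute. At log-SD 0.4 the covariate alone gives 17 points (61% to 78%) and the log scale adds 5 more.

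**Low spread.** At log-SD 0.3 the two ends of the table are about 86–87% and 97%. At lower spread both approach 100%.

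**40 per group.** Raw change against the log-scale adjusted analysis: about 96% against more than 99%, 64% against 90%, and 36% against 69%.

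**Type I error.** It stays near 5% on every scale with equal groups. On raw skewed values at 15 per group it is 3.9% to 5.0%, so slightly conservative if anything.

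**Direction matters.** The table is for a fall, which is the hoped-for direction for insulin and triglycerides. The synopsis treats a suppressed SAM/SAH as the disease state, so there the hoped-for change is a rise. For a rise, with effects sized for 80% nominal power on log change and 15 per group, raw against log change is 77% against 77% at a coefficient of variation of 0.5 (log-SD √ln 1.25 = 0.47), and 66% against 77% at 1.0 (log-SD √ln 2 = 0.83). The log scale by itself therefore gains less for SAM/SAH unless its spread is large.

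**Week 12 alone.** If the ANOVA were read as a comparison at week 12 only, with the effect again sized for 80% nominal power and 15 per group, log-scale power is about 77%. Raw-scale power is 76%, 75%, 73%, 67% and 62% at coefficients of variation 0.2, 0.3, 0.5, 0.8 and 1.0.

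**The case against.** **The scale is not stated, and a statistical analysis plan could set it.** This is fair as far as it goes. Analysis in measured units is the natural reading of ANOVA and paired t-tests on named measures, but it is an inference. The sentence on mean scores follows the cognitive tests and may not cover the laboratory measures. What stands against the objection is that the protocol does name its method, and a better one exists that uses only data already collected.

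**The skewness is assumed.** True. Nothing in the protocol shows how dispersed these measures will be, and SAM/SAH in particular may vary little. The gain shrinks as spread falls. The calculation also covers two visits, not the five planned for triglycerides.

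**A difference in arithmetic means is a legitimate target.** Also true. The argument is about efficiency, not validity.

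Two stronger readings are tempting, and the documents do not support them.

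- A reader might infer that a few extreme values decide the result. At 15 per group with a real effect, removing the single largest week-12 value changes the verdict in 11–14% of simulated trials on the raw scale and 10–12% on the log scale. That is about 1 to 4 points of added fragility, with no inflation of type I error.
- A reader might infer that the SAM/SAH verdict hangs on an arbitrary choice of numerator. Arithmetic means are indeed not invariant to inversion: ratios 1 and 9 average 5, while their inverses average 0.56 and not 0.20. But the protocol writes the ratio as SAM/SAH throughout, so no such choice is open. A test of the inverse is one that nobody plans.

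**Conclusion.** The concern holds as a point of efficiency. As written, the plan is valid for type I error. Under the natural reading in measured units, it gives up about 15 to 22 points of power at 15 per group for a 30% reduction when the log-SD is 0.4 to 0.8, compared with a log-scale analysis adjusted for week 0. The loss is about 10 points at log-SD 0.3 and fades below that. For SAM/SAH, where a rise is hoped for, the contribution of the log scale is smaller.

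All of these figures depend on assumed log-normality, spread, effect and correlation, none of which the protocol supplies. The severity is low.

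**What to change.** In the Research Method section, state that SAM/SAH, fasting insulin and fasting triglycerides will be compared between groups on the log scale, with the log week-0 value as covariate. Results are reported as geometric-mean ratios with 95% confidence intervals. For triglycerides, week 0 becomes the covariate and the later visits the outcome. Any paired t-test on these three measures should use the same scale.

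HgA1c and the cognitive scores can stay on their own scales. For fasting glucose, whole blood histamine and ketones, state the intended scale too, before any results by group are seen.

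The cost is a few sentences: no added subjects, visits or assays. The downside is that effects are read as percentage differences instead of differences in laboratory units.

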#### Risk / Safety Information

- There are few foreseeable risks associated with this study. No costs are associated with participation nor will the subjects' decision to participate affect their employment/medical care or insurance status. Discomfort associated with study participation may include short-term general malaise commonly associated with dietary changes (if the subject is in the experimental group). Discomfort during blood draws at North Memorial Reference Laboratories may also occur. If subjects experience any discomfort, they will be instructed to inform the phlebotomist immediately. This study is considered to have minimal risk.
- The benefits which may reasonably be expected to result from this study are improved memory as measured by cognitive assessments (MoCA, BVMT-R, and Rey Auditory Verbal Learning Task), reversal of MetS, improved blood lipid biomarkers, decreased HgA1c, increased blood ketone levels, and reduced weight and body fat mass.

#### Monitoring and reporting of Adverse Events/Serious Adverse Events

- Subjects will receive instructions to contact the principal investigator or sub-investigator for nutritional counsel if they experience general malaise or any discomfort when changing dietary protocol.
- Subjects will receive instructions to inform the phlebotomist at North Memorial Reference Laboratory if they feel any discomfort during blood collection.
- If a subject presents with an adverse effect from following the study protocol, they will be referred back to their primary care physician in order to determine if continued study participation is recommended. Subjects will only be allowed to continue with the study with written permission from their primary care provider.
- Any unanticipated problems will be reported to the IRB within (10) calendar days of being reported to the investigator.

#### Study Oversight

- The principle investigator ([name]) will provide all oversight for the project and supervision all study activities.
- The only other person who will have access to subjects is sub-investigator ([name]).
- The Investigator will ensure that all study staff are adequately trained in the study protocol

- Both [name] and [name] have received NIH certification: "Protecting Human Research Participants"

### **Certificate of Completion**

The National Institutes of Health (NIH) Office of Extramural Research certifies that [name] successfully completed the NIH Web-based training course "Protecting Human Research Participants".

Date of completion: 07/30/2017.

Certification Number: 2442927.

- Data Management
  - Who will be collecting, analyzing the data? [name] & [name]
  - Do you plan to have an independent data analysis? Yes, through the University of Minnesota ([name] and [name])
  - Data retention (i.e. how long so you plan to maintain records for this study) – 2 years post study
- IRB Review / Ethics / Informed Consent
  - Explain your informed consent process.
    1. Subjects will be given the informed consent during an individual intake meeting (after being referred by their primary care provider).
    2. Subjects will be provided with the opportunity to take the informed consent home to discuss with their families.
    3. [name] or [name] will explain the informed consent and answer any questions.
    4. Once the subject signs the consent, they will receive a copy of the signed consent for their records.
- Confidentiality
  - Discuss the procedures that will be used to maintain the **confidentiality of the research data**. Specifically, **how will data be stored to ensure that it is secure and remains confidential?**

- Research data will be used for the purposes of this study only. Copies of medical and clinical measures will be stored in a locked file at Bristlecone Health, Inc. and will only be accessed by [name] and [name] (co-investigator). If a subject decides to withdraw from the study, his/her confidential medical data and clinical measures will be destroyed within 24 hours of receipt of the written request to withdraw from the study
- Data collection and reporting for the purposes of this study will remain confidential and subject identity will not be identifiable. Each subject will be given a unique ID code for the purposes of data analysis. Upon completion of the study, subjects have 8 weeks to obtain a copy of their clinical data measures. The data will be retained for 2 years post study.
- Data may be published in certain journals. Upon publication of the aforementioned study, all protected health information (PHI) will be protected and subjects' identities will not be disclosed in the publication or any other forum.
